4.5 Missing and Partial Data

In general, other than for partial dates, missing data will not be imputed and will be treated as missing. The algorithms for imputation of partial dates vary depending upon the parameter. These are presented in Appendix A.

4.6 Safety Observation Periods

Generally only the safety data (including adverse events that start or worsen, laboratory results, vital signs, ECGs, ECOG PS, concomitant medications, etc.) reported during a safety observation period (defined below) will be analyzed and summarized, unless otherwise specified in this plan.

4.6.1 Standard Observation Period

Two standard safety observation periods are defined: one for the Core period and one for Crossover period.

Core Treatment Period: the standard safety observation period is the interval from the first dose date of original study treatment to the earliest of:

- Date of last dose of last component of original study treatment + 30 days or
- Date of death or
- Date subject withdrew consent for non-interventional study assessments or
- Data cutoff date (for a particular analysis) or
Date of enrollment in the Crossover Phase - 1

Crossover Treatment Period: the standard safety observation period is the interval from the first dose date of crossover study treatment to the earliest of:

- Date of last dose of last component of crossover study treatment + 30 days or
- Date of death or
- Date subject withdrew consent for non-interventional study assessments or
- Data cutoff date (for a particular analysis)

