3.5.1. Treatment Discontinuation

Subjects will receive study treatment until treatment discontinuation for any of the reasons listed below. Subjects may discontinue study treatment and assessments or withdraw their consent to participate in the study at any time without prejudice. If a subject discontinues study treatment, the reason will be documented in source documents and all study treatment will be stopped. The Investigator may also discontinue a subject from study treatment if in his or her clinical judgment it is in the best interest of the subject or if the subject cannot comply with the protocol. In addition, the investigator will also discontinue a subject from study treatment upon the Sponsor's request or if the Sponsor chooses to terminate the study.

Furthermore, any of the following conditions require withdrawal of the subject from study treatment:

- Unacceptable side effects the Investigator feels may be due to study treatment. Continuation of one component of the combination study treatment while discontinuing the other will be allowed. The Investigator is encouraged to consult with the Sponsor before discontinuing subjects from study treatment.
- Subject participation in another clinical study using an investigational agent, investigational medical device, or other intervention.
- Necessity for treatment with nonprotocol systemic anticancer therapy.
- Necessity for interrupting all study treatment for greater than 12 weeks for study-treatment related AEs unless approved by the Sponsor. (Note: temporary interruptions of study treatment for greater than 12 weeks due to the effects of COVID-19 and unrelated to AEs are described in [Appendix M](#))
- Refusal of sexually active fertile subjects (excluding subjects who have been sterilized) to use highly effective methods of contraception ([Appendix H](#)).
- Female subjects who become pregnant.
- Request by the Sponsor.
- Significant noncompliance with the protocol schedule in the opinion of the Investigator or the Sponsor.

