9.6.1. Adverse Events

Adverse event terms recorded on the CRFs will be mapped to preferred terms using the Medical Dictionary for Regulatory Activities (MedDRA). The Investigator will classify the severity of AEs using CTCAE v5 and will judge each event to be “not related” or “related” to study treatment.

A treatment emergent adverse event (TEAE) is defined as any event that begins or worsens on or after the date of first dose of study treatment. Only TEAEs with an onset date prior to date of decision for treatment discontinuation (defined as the later of the date of the decision to permanently discontinue study treatment or the date of the last dose of study treatment) + 30 days (+ 100 days for SAEs and certain other AEs; [Section 8.3](#)) will be tabulated in summary tables.

The frequency and percentage of subjects with TEAEs will be tabulated for overall incidence by system organ class and/or preferred term by treatment arm. Related TEAEs, serious TEAEs, related serious TEAEs, high-grade TEAEs, Grade 5 TEAEs, and TEAEs resulting in study treatment discontinuation will be similarly summarized. Summaries by worst reported severity for each event within a subject will also be provided.

At each level of summarization, a subject will be counted only once for each AE preferred term he/she experiences within that level (ie, multiple episodes of events with the same preferred terms will be counted only once).

All reported subject deaths will be summarized by treatment group, cause of death, and relationship to study treatment.

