4.2 Definition of Baseline

In general, for efficacy endpoints the last observed measurement prior to randomization will be considered the baseline measurement.

For safety endpoints the last observation before first dose of study treatment will be considered the baseline measurement unless otherwise specified and will be established for each period defined in Section 4.6.

For assessments on the day of first dose of study treatment where time is not captured, if such procedures are required by the protocol to be conducted before first dose or a nominal pre-dose indicator is available, this will serve as sufficient evidence that the assessment occurred prior to first dose.

For the experimental arm (cabozantinib + atezolizumab treatment), the earliest instance of administration of either cabozantinib or atezolizumab on the study will be considered as the time point of first dose. Similarly, the latest instance of administration of either of the treatments will be considered as the time point of last dose.

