4.6.2 Extended Observation Period

To evaluate the incidence of adverse events of special interest (AESIs), extended observation periods are defined for summarizing safety data as below.

Core Treatment Period:

- Date of last dose of last component study treatment + 100 days or
- Date of death or
- Date subject withdrew consent for non-interventional study assessments or
- Data cutoff date for analysis under consideration

Crossover Treatment Period:

- Date of last dose of last component study treatment + 100 days or
- Date of death or
- Date subject withdrew consent for non-interventional study assessments or
- Data cutoff date for analysis under consideration or
- Date of initiation of maintenance phase -1

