6.5 Study Treatment Exposure

Study treatment exposure will be summarized descriptively and will include subjects in the P-Safety and Safety populations. Due to different treatment types (infusion vs. oral tablet) and frequency of administration (q3wk vs daily) between atezolizumab and cabozantinib, the exposure summaries for cabozantinib and atezolizumab will be presented separately along with summary for study treatment exposure. The study protocol allows subjects on the combination treatment to discontinue one component of the combination treatment but continue to receive the other component. Date of discontinuation along with reason for discontinuation will be recorded on separate CRFs for cabozantinib and atezolizumab treatment components. Duration of cabozantinib is defined as time from first dose to date of decision to discontinue and duration of atezolizumab is defined as time from first dose to date of last dose. Inclusion of the various treatment arms in the presentation of exposure summaries are described in Section 4.6.

For the combination regimen (experimental arm) an overall summary will be provided as follows:

- Duration (in months) of exposure, defined as maximum of duration of cabozantinib exposure and duration of atezolizumab exposure, calculated as maximum of [(date of decision to discontinue cabozantinib/cut-off date – date of first dose of cabozantinib + 1) /30.4375 and (last dose date of atezolizumab – date of first dose of atezolizumab + 1) /30.4375]
- The number and percent of subjects for who received at least one non-zero dose of cabozantinib > 4 weeks after last dose of atezolizumab.
- The number and percent of subjects for who received at least one dose of atezolizumab > 4 weeks after non-zero dose of cabozantinib.

The other summaries for cabozantinib and atezolizumab given in combination will present each agent separately as the former is an oral drug and the latter is an infusion drug.

The following independent summaries will be provided for cabozantinib 40 mg (as part of combination), cabozantinib 60 mg (as a single agent) and sorafenib. The start and end dates refer to the respective individual agent.

- Duration (in months) of exposure, including dose holds, calculated as (date of decision to discontinue study treatment/cut-off date – date of first dose + 1) /30.4375
- Average daily dose (mg/day) of study treatment, calculated as (total mg received / duration of exposure in days)

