8.1 Adverse Events

Adverse event terms recorded on the CRF will be mapped to preferred terms and system organ class using the Medical Dictionary for Regulatory Activities (MedDRA). The severity of AEs will be measured by CTCAE ((Common Terminology Criteria for Adverse Events, version 5.0, 2017)) guidelines. The investigator will judge each event to be “not related” or “related” to study treatment. For subjects in the experimental arm, the investigator will judge each event’s relationship to study treatment, separately for cabozantinib and atezolizumab. However, in summarizing relationship of study treatment to adverse events in the experimental arm, relationship to either cabozantinib or atezolizumab will be considered as related to the experimental arm.

A TEAE is defined as any event with an onset date on or after the date of the first dose of study drug or any ongoing event on the date of the first dose of study drug that worsens in severity after the date of the first dose of study drug. In the Crossover phase, subjects who cross over to receive the experimental treatment, this definition will be with respect to the first dose of the experimental treatment received.

Unless otherwise specified, only TEAEs with an onset date (or date of increase in severity) through the end of the relevant safety observation period (see Section 4.6) will be tabulated in summary tables.

All deaths after informed consent, irrespective of when they occur, are classified as Grade 5 TEAEs. However, only those associated with an event starting after informed consent through 100 days after the date of the decision to discontinue the last component study treatment (or

starting at any time after informed consent and judged to be related to study treatment) required reporting as an SAE.

For the purpose of calculating treatment emergence and inclusion in summary tables, incomplete onset dates will be imputed as detailed in Appendix A. The calculations of percentages will be based on original unrounded values.

Summaries of AEs leading the changes in study treatment (e.g. leading to dose hold, reduction, modification, and/or discontinuation) will be based upon the fields for actions taken with each agent, collected on the AE CRF, e.g.

- Summaries of AEs leading to hold of oral treatment will include records where the “action taken” with cabozantinib or sorafenib = dose hold

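### SAP adverse-event windows run from last dose alone, while protocol 9.6.1 runs them from the later of last dose and discontinuation decision, so the standard tables omit some collected events after a terminal hold

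*SAP*

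**What the plan says.** **Protocol.** Section 9.6.1 limits the summary tables as follows: "Only TEAEs with an onset date prior to date of decision for treatment discontinuation" plus 30 days, or plus 100 days for SAEs and certain other AEs, with a cross-reference to the AESI section (8.3). It defines the anchor as whichever comes later, the discontinuation decision or the last dose. Collection uses the same anchor (protocol 8.1.1 and 8.4, and the end-of-treatment date defined in Appendix K).

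**SAP.** Section 4.6.1 ends the Core standard period at the earliest of several dates. The treatment-based one is "Date of last dose of last component of original study treatment + 30 days". The Crossover equivalent is "Date of last dose of last component of crossover study treatment + 30 days". Section 4.6.2 does the same for the extended period: "Date of last dose of last component study treatment + 100 days". Last dose cannot be read as the decision date, because for the experimental arm SAP 4.2 states that "the latest instance of administration of either of the treatments will be considered as the time point of last dose". SAP 8.1 then tabulates, unless otherwise specified, "only TEAEs with an onset date (or date of increase in severity) through the end of the relevant safety observation period", and the standard period is the default for the overall AE summary and most TEAE tables.

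**Change control.** SAP 4.9 requires substantive departures from the protocol's analyses to be documented in a revised plan. The SAP does not mention this one, and its addendum deals only with event counts above plan in the time-to-event analyses.

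**The concern.** The two documents give different end dates for the same tables whenever treatment is held and then stopped without another dose. The protocol keeps such a subject under observation: scheduled assessments continue during a hold (Appendix A), and protocol 5.2 asks for additional safety assessments, at least weekly, when the hold is for AEs. The SAP window can therefore close during a period that the protocol watches closely and from which AEs are on the CRF.

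At stake is whether reported TEAE incidence, including Grade 3/4 incidence in the standard-period tables, matches the protocol's definition. The omission could also differ by arm. In the combination arm the clock starts only when the last component has been given for the last time, so both drugs must be off. In the two single-drug arms one hold is enough.

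**Working it through.** **Inputs**
- SAP window ends: last dose + 30 days (4.6.1) and + 100 days (4.6.2).
- Protocol window ends: later of decision and last dose, + 30 and + 100 days (9.6.1).
- Longest hold before discontinuation is required: protocol 3.5.1 lists as a reason for withdrawal from treatment "Necessity for interrupting all study treatment for greater than 12 weeks for study-treatment related AEs unless approved by the Sponsor". 12 weeks × 7 = 84 days.
- The documents give no distribution for the time from last dose to decision, so it is varied from 0 to 84 days.

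**Formulae.** Let L = decision date − date of last dose of the last component, with L ≥ 0. Count days from last dose and treat both window ends as inclusive. (Read strictly, the protocol asks for onset before its end date, which would take one day off its window.)
- Standard: SAP ends at day 30, protocol at day L + 30. Omitted: days 31 to L + 30, which is L days.
- Share of the protocol's post-last-dose window omitted: L / (L + 30).
- Omitted days that precede the decision itself: max(0, L − 30).
- Extended: SAP ends at day 100, protocol at day L + 100. Omitted: L days.

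| L (days) | Protocol end (day) | Omitted days | Share | Before decision |
|---|---|---|---|---|
| 0 | 30 | none | 0% | 0 |
| 7 | 37 | 31–37 | 7/37 = 19% | 0 |
| 21 | 51 | 31–51 | 21/51 = 41% | 0 |
| 42 | 72 | 31–72 | 42/72 = 58% | 12 |
| 84 | 114 | 31–114 | 84/114 = 74% | 54 |

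At L = 84 the extended window ends at day 100 in the SAP and day 184 in the protocol (84/184 = 46% omitted). Days 101 to 114, which is 14 days of the protocol's 30-day window, then lie outside even the SAP's extended period.

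The protocol itself contains a route to L = 42. Table 13 interrupts cabozantinib for Grade 3 palmar-plantar erythrodysesthesia and stops treatment if there is no improvement within 6 weeks. How many subjects would take that route is not stated.

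**Where the omitted events can still appear under the SAP**
- At any time: TEAEs leading to discontinuation, related SAEs, related Grade 5 events (8.1).
- Up to last dose + 100 days: SAEs, Grade 5 events (8.1) and AESIs (8.3).
- Regardless of timing: all deaths (8.2), and the listing of all AEs (8.1).

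What remains untabulated is mainly (a) non-serious, non-AESI events that did not lead to discontinuation, with onset on days 31 to L + 30, and (b) unrelated SAEs and AESIs with onset on days 101 to L + 100.

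**After the fix.** With the later-of anchor, the SAP windows end at L + 30 and L + 100, and the omission is 0 days for every L.

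**The case against.** The best defence is that the gap is narrow. It needs a terminal hold of every component; a hold followed by any further dose loses nothing. The 84 days is a ceiling (absent Sponsor approval for longer), not a typical value. Tables count each subject once per preferred term (protocol 9.6.1), so an event in the gap raises incidence only if that subject had not already had the term, or had it at a lower grade. All of this stands, and days lost should not be read as incidence lost.

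The SAP also states that it is based on protocol amendment 2.0, whereas the protocol reviewed here describes amendment 3.0 changes. Whether section 9.6.1 read the same way when the SAP was written cannot be seen. That leaves the origin of the mismatch open, but the current documents still disagree.

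A reader might infer more than the documents support:
- *That laboratory, vital-sign, ECOG and ECG summaries also contradict the protocol.* SAP 8.4 to 8.7 use the same window, but protocol 9.6.2 and 9.6.3 set no end date for those data.
- *That Grade 5 reporting as a whole is understated.* Only the window-limited tables are affected; any-time related Grade 5 tables and the summary of all deaths remain.
- *That adverse-event rates are diluted because hold time counts as exposure.* SAP 6.5 does say "Duration of cabozantinib is defined as time from first dose to date of decision to discontinue", but SAP 8.1 plans counts and percentages rather than exposure-adjusted AE rates, and exposure excluding holds is also reported.
- *That the window is too short after a three-weekly infusion* (30 − 21 = 9 days past the next due dose). No arm receives atezolizumab alone and cabozantinib is daily, so this applies only where cabozantinib stopped first.
- *That the omission favours a particular arm.* It may differ by arm, but nothing in the documents gives its direction or size.

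**Conclusion.** The mismatch is real, and no justification is recorded. Whenever the discontinuation decision comes L days after the last dose of all components, the SAP's standard-period TEAE tables omit L days of events that protocol 9.6.1 says will be tabulated, and the extended-period tables lose the same L days. The upper bound is 84 days (day 30 against day 114, and day 100 against day 184) unless the Sponsor approves a longer interruption; at L = 0 there is no loss. These figures are date arithmetic and assume only the two anchor definitions. The effect on incidence cannot be estimated from the documents and is likely smaller than the day counts suggest. The practical consequence is confined mainly to the two residual groups (a) and (b) identified above. The efficacy tests are untouched.

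**What to change.** In SAP 4.6.1 and 4.6.2, for both Core and Crossover and for the TEAE, SAE and AESI tables, replace the last-dose anchor with the later of (i) the date of the decision to discontinue all study treatment permanently and (ii) the date of last dose of the last component. Keep the 30 and 100 days.

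At the same time, add the day before Crossover Phase enrollment as a stop condition for the Core extended period. SAP 4.6.1 has this stop and 4.6.2 does not, so a later anchor could lengthen an overlap with the Crossover Period.

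Laboratory, vital-sign, ECOG and ECG summaries may follow the same window for consistency, though the protocol does not require it. SAP 7.5.11 takes person-years for resource use from the safety observation period, so the revision should say which window applies there. The death-timing categories in SAP 8.2 stay anchored on last dose and should be labelled as such.

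If the last-dose anchor was intended, the alternative is to document it under SAP 4.9 with a reason and add a sensitivity tabulation on the protocol window.

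The cost is revised SAP wording and one changed derivation, on data already collected. The downside is a slightly higher reported AE incidence.

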4.6.2 Extended Observation Period

To evaluate the incidence of adverse events of special interest (AESIs), extended observation periods are defined for summarizing safety data as below.

Core Treatment Period:

- Date of last dose of last component study treatment + 100 days or
- Date of death or
- Date subject withdrew consent for non-interventional study assessments or
- Data cutoff date for analysis under consideration

Crossover Treatment Period:

- Date of last dose of last component study treatment + 100 days or
- Date of death or
- Date subject withdrew consent for non-interventional study assessments or
- Data cutoff date for analysis under consideration or
- Date of initiation of maintenance phase -1

4.7 Definition of Prior, Concomitant, and Subsequent Therapy

For the purpose of inclusion in summary tables, incomplete medication or radiation start and stop dates will be imputed as detailed in Appendix A. Based on imputed start and stop dates:

- Prior medications/radiation therapies are defined as medications with a stop date occurring before the date of first dose of study treatment.
- Subsequent medications/radiation therapies are defined as those that start after the date of randomization.
- Concomitant medications/radiation therapies are defined as medications that stop or continue on or after date of first dose day through the end of safety observation period.

Medications/radiation therapies may be summarized as prior, concomitant and/or subsequent.

4.8 Software

All analyses will be conducted using SAS Version 9.3 or higher.

4.9 Changes to Planned Analyses

Substantive changes to the analyses described in the protocol or in approved versions of this plan will be fully documented in a revised version of this plan approved by the Sponsor prior to conducting analyses that may be potentially impacted by said changes.

Clarifications, minor corrections, and operational considerations necessary to accurately conduct the analyses that do not materially change the nature of the analysis will be documented in an addendum to this plan that will be also be approved by the Sponsor prior to final study analyses.

Minor typographical error in the protocol are corrected in Table 11 of this plan.

5 STUDY POPULATION SUMMARIES

5.1 Enrollment

Subjects are defined to be enrolled at randomization. Enrollment will be summarized by region, country, site, and protocol version for the PITT and ITT populations.

5.2 Disposition

Subject disposition will be summarized categorically and will include the number and percentage of subjects in the ITT, PITT, P-Safety and Safety populations.

The reasons for each study treatment discontinuation, discontinuation of radiographic follow-up and study follow-up discontinuation will also be summarized categorically. Additional summaries of the combination arm will also be provided to characterize the status and nature of subjects discontinuing treatment components due to AE.

All screen failure subjects will be summarized with the reason for screen failure.

